5.1 Overview

The LLINs will be distributed according to detailed national guidelines, which build on prior experience from a similar net distribution campaigns carried out in 2013-2014 and 2017-18, incorporated guidance for LLIN distribution in the context of COVID-19, and lessons from food distribution during COVID-19. The overall goal of the 2020 LLIN distribution campaign is to reduce malaria morbidity and mortality in Uganda by achieving universal coverage with LLINs, aiming to ensure that: (1) 85% of the targeted population has access to a LLIN, and (2) 85% of LLINs distributed are utilised. Members of the research team will engage with Uganda's national committees that are coordinating the LLIN universal coverage campaign, including the National Coordination Committee (NCC), which will be responsible for overall coordination and oversight of campaign planning, implementation, and engagement with political and traditional authorities, the operations sub-committee, the logistics sub-committee and the advocacy, communication and social mobilisation sub-committee. All LLINs procured for the campaign will be stored centrally in at the National Medical Stores warehouses in Entebbe and will be distributed across the country in waves. The 32 districts selected for this study are included in Waves 3-5 and are scheduled to receive nets from October 2020 to February 2021, although the timelines are subject to change depending on procurement and importation of the LLINs. The research team will work closely with the NCC and other stakeholders to ensure that the nets are allocated per the randomisation scheme.

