13.5 Analytical plan

All analyses will be conducted using an intention-to-treat approach. For our primary outcome, we will compare cluster level estimates of the incidence of malaria between intervention and control arms using a mixed effects Poisson regression model since randomization will occur at the district level (each district will include two clusters, randomized to the two study arms). We will also adjust our model for baseline estimates of malaria incidence (3 months prior to the intervention) and additional cluster-level covariates from the cross-sectional surveys including treatment seeking behaviour (to account for cases of malaria not captured at the MRCs) and the diagnostic accuracy of RDTs vs microscopy (to account for differences in the use of these diagnostic tests between clusters). The effect of the intervention will be expressed as an incidence rate ratio (incidence in the intervention arm/incidence in the control arm). Our primary analysis will evaluate malaria incidence over 24-months following the intervention. We will also perform secondary analyses of malaria incidence stratified by time following the intervention (year 1 vs year 2).

For our secondary outcomes, comparisons between intervention and control arms will be made using an individual-level approach to the analysis due to the large number of clusters per arm. Prevalence measures (parasitaemia, anaemia, LLIN ownership, LLIN coverage, LLIN access and LLIN use) will be compared using mixed effects logistic regression models with random effects at the level of the cluster and household. The effect of the intervention will be expressed as the prevalence ratio (prevalence in the intervention arm/prevalence in the control arm). For comparison of vector density, LLIN integrity, and bio-efficacy (funding permitting) between treatment arms, regression models will be used with generalized estimating equations to allow for within-cluster correlations. The effect of the intervention will be expressed as the density or rate ratio (density or rate in the intervention arm / density or rate in the control arm). Chemical analysis of withdrawn LLINs and their unused controls will be compared using the Wilcoxon rank sum test.

14 Ethical considerations

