### 3.3 Cluster randomisation

Given the open-label study design and the need to generate estimates of the targeted number of LLINs for distribution in advance, randomisation was completed at the time of the protocol development. The randomisation was carried out by a member of the study team who is not based in Uganda and not directly involved in the field work. The unit of randomisation (cluster) was at the level of the MRC and the surrounding sub-county targeted for LLIN distribution. Randomization was done in blocks of 2, with each block representing a district containing 2 clusters with one cluster assigned the letter "A" and one cluster assigned the letter "B". For each block, a random number between 0 and 1 was generated using the 'runiform' command in STATA (StataCorp, Texas, USA). If the random number was  $<0.5$ , cluster "A" was assigned to PBO LLINs and cluster "B" was assigned PPF LLINs. If the random number was  $\geq0.5$ , cluster "A" was assigned to PPF LLINs and cluster "B" was assigned PBO LLINs. The final treatment allocations are summarized in Table 1, and the full intervention allocation list is provided in Appendix A.

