## **6.1 Primary outcome**

Our sample size of 32 clusters per arm was calculated to detect a 26% decrease (incidence rate ratio (IRR) = 0.74) in the incidence of malaria over the 24 month period following the intervention (the primary endpoint of the study) between the two study arms, given a power of 80% and a two-sided significance level of 0.05. This sample size calculation assumes an incidence of 332 malaria cases per 1000 person-years in the control arm and a coefficient of variation (CV) of 0.42 calculated from the 14 MRCs where estimates of malaria incidence are available over the last 6 month at the time of protocol development.

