## **6.2 Secondary outcomes**

We will sample all eligible children aged 2-10 years from 50 households in the 64 clusters in each round of surveys, aiming to maximise the potential prevalence ratio detectable in the intervention arm, as well as the cost/value of the trial. Assuming an average of 1.8 children aged 2-10 years per household, we estimate that we will survey 5,760 children from 3,200 households. Assuming a coefficient of variation of 0.4, across a wide range of prevalence measures in the control arm (10-70%) our sample size will allow us to detect a 25-28% decrease in the prevalence measure of interest (prevalence ratio (PR) = 0.72-0.75), given a power of 80% and a two-sided significance level of 0.05.

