#### 8.1.1 Analytical approach

All analyses will be conducted using an intention-to-treat approach according to the treatment allocations the clusters were randomized to. We will compare cluster level estimates of the incidence of malaria

between the intervention (PPF LLINs) and control arm (PBO LLINs) using a mixed effects Poisson regression model with a random effect at the district level (each district includes two clusters, randomized to one of the two study arms) and adjustment for log-transformed estimates of the baseline malaria incidence (3 months prior to the intervention) for each cluster. The effect of the intervention will be expressed as an incidence rate ratio (incidence in the intervention arm/incidence in the control arm). Our primary analysis will evaluate malaria incidence over 24 months following the intervention. We will also perform secondary analyses of malaria incidence stratified by time following the intervention (year 1 vs. year 2) and after adjusting for additional cluster-level covariates from the cross-sectional surveys including treatment seeking behaviour (to account for cases of malaria not captured at the MRCs) and the diagnostic accuracy of RDTs vs microscopy (to account for differences in the use of these diagnostic tests between clusters). These models will include random effects at the cluster level and we will assess the need for an additional random effect at the District level.

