### 8.2.1 Analytical approach

All analyses will be conducted using an intention-to-treat approach according to the treatment allocations the clusters were randomized to. Separate analyses will be conducted for the 12 and 24 month cross-sectional surveys. We will compare individual level estimates of the prevalence of parasitemia and anemia between the intervention (PPF LLINs) and control arm (PBO LLINs) using a mixed effects logistic regression model with random effects at the level of the cluster and household. We will compare household level estimates of LLIN ownership, coverage, and use using a mixed effects logistic regression model with a random effect at the level of the cluster. Effects of the intervention will be expressed as odds ratios (odds in the intervention arm/odds in the control arm).

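### The survey-outcome models omit district, the randomisation block, and baseline incidence, although the primary model has both; if clusters within a district are alike, available precision is lost

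*SAP*

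**What the plan says.** SAP 3.3 describes a pair-matched design: "Randomization was done in blocks of 2, with each block representing a district containing 2 clusters". There are 32 pairs, so 32 clusters per arm.

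The primary analysis respects this. SAP 8.1.1 specifies a "mixed effects Poisson regression model with a random effect at the district level" and adjusts for the log of each cluster's incidence in the three months before the intervention. Protocol 13.5 links its choice of primary model to randomisation within districts.

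The survey outcomes are treated differently:

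- Parasitaemia and anaemia (SAP 8.2.1): a "mixed effects logistic regression model with random effects at the level of the cluster and household".
- LLIN ownership, coverage and use (SAP 8.2.1): "a mixed effects logistic regression model with a random effect at the level of the cluster".
- All prevalence outcomes (Protocol 13.5): "mixed effects logistic regression models with random effects at the level of the cluster and household".

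SAP 9.2 names covariates for the primary outcome only. SAP 8.1.1 ends by saying that the need for a further district random effect will be assessed. That sentence follows the secondary analyses of incidence, so it does not reach the survey models.

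**The concern.** The survey data come from the same clusters, pairs and allocation as the incidence data, and neither document explains why the pairing is used in one analysis and dropped in the other.

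In a paired design, variation between districts cancels from the arm comparison. A model with cluster effects only cannot separate it out. It absorbs district variation into the cluster variance and carries it into the standard error of the arm effect. With positive within-district correlation, that standard error is too large. The risk is therefore of missing a real difference in parasitaemia or anaemia, the outcomes of the first secondary objective.

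**Working it through.** **Inputs from the documents.** 32 clusters per arm in 32 district pairs (SAP 3.3, 6.1). In SAP 6.2: 5,760 children / 64 clusters = 90 per cluster (m), coefficient of variation k = 0.4, control prevalence 10–70%, detectable prevalence ratio (PR) 0.72–0.75, 80% power, two-sided 0.05.

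**Assumed.** ρ, the district share of between-cluster variance (the within-district correlation of true cluster prevalence), shown from 0 to 0.6. Control prevalence is set at 20%.

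**1. The plan's own figure.** The standard unmatched cluster-trial formula is

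c = 1 + (1.96 + 0.84)² V / (p0 − p1)², with V = p0(1−p0)/m + p1(1−p1)/m + k²(p0² + p1²).

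At p0 = 0.20 and PR 0.72, p1 = 0.144:

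- V = 0.001778 + 0.001370 + 0.16 × (0.04 + 0.020736) = 0.012865.
- c = 1 + 7.849 × 0.012865 / 0.056² = 33.2, close to the 32 planned.

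Solving for 32 clusters gives a detectable PR of 0.715 at 20% prevalence and 0.744 at 70%. The upper end of the stated range is reproduced. At 10% prevalence the formula gives 0.680, so 0.72 is not reproduced there; that is a separate matter. The formula has no pairing term, so the stated power does not depend on pairing.

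**2. How far the standard error is overstated.** The true variance under pairing is V − 2ρk²p0p1, where 2k²p0p1 = 2 × 0.16 × 0.20 × 0.144 = 0.009216. A cluster-only model reports a variance based on V.

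| ρ | V − 0.009216ρ | Reported SE / true SE |
|---|---|---|
| 0.2 | 0.011022 | 1.08 |
| 0.4 | 0.009179 | 1.18 |
| 0.6 | 0.007335 | 1.32 |

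**3. Cluster-level tests, simulated (20,000 trials per power figure).**

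| ρ | Type I error, unpaired | Type I error, paired | Power at PR 0.72, unpaired | Power at PR 0.72, paired |
|---|---|---|---|---|
| 0 | about 5% | about 5% | 79% | 78% |
| 0.2 | 3.2% | about 5% | 81% | 84% |
| 0.4 | 1.7% | about 5% | 83% | 90% |
| 0.6 | 0.9% | about 5% | 86% | 96% |

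**4. Fitted logistic mixed models.** These used maximum likelihood and 1,500 trials per scenario. The household effect was left out, so this simplifies the SAP model. Power is at PR 0.75, a smaller effect than the 0.715 detectable at this prevalence. The power levels are therefore not evidence against the plan's power claim; the contrast between models is what matters.

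| ρ | Cluster only (z): SE / empirical SD | Cluster only (z): type I error | Cluster only (z): power | With district (t, 31 df): type I error | With district (t, 31 df): power |
|---|---|---|---|---|---|
| 0 | 0.98 | 6.7% | 65% | 6.0% | 64% |
| 0.2 | 1.08 | 3.7% | 65% | 4.9% | 69% |
| 0.4 | 1.19 | 2.7% | 66% | 5.1% | 77% |
| 0.6 | 1.33 | 1.1% | 70% | 5.5% | 88% |

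The standard-error ratios agree with step 2. With the district effect but an ordinary z test, type I error is 6.1–7.3%, so the t reference matters.

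**5. Baseline covariate.** This takes the paired analysis at ρ = 0.4, where power is about 82%, the level that a paired test gives at PR 0.75. Adding a covariate whose correlation with cluster prevalence is 0, 0.3, 0.5 or 0.7 (assumed) gives 81%, 82%, 86% or 93%. A second simulation, in which the covariate also carries the district component, gave 81%, 82%, 85% and 89%.

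**The case against.** The strongest reply is that this is optional efficiency. Ignoring the pairs does not bias the estimate, the unpaired model matches the basis of the stated power, and these are secondary outcomes. That is correct, and it limits how serious the point is.

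The size also rests on a correlation that the documents do not give. The regional range of 8.0–53.1% (Protocol 1.3) comes from an earlier survey that was not restricted to this trial's high-transmission districts without IRS. Comparable level of care within a district was only an aim: in Protocol Table 2, 19 of the 32 pairs join an HC IV with an HC III. At a low correlation of 0.1, pairing gains only about a point. So the size stays conditional, but the worst case is a loss of one to two points.

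Three further points stand in part:

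- At zero correlation the cluster-only z test rejected 6.7% under the null, so the test is conservative only when the correlation is appreciable.
- The figures use 90 children aged 2–10. Anaemia covers ages 2–4. With an assumed 30 children per cluster, the gain at PR 0.72 is about 3, 6 and 12 points. LLIN outcomes were not simulated.
- Baseline incidence is not part of the pairing, and it helps only if it correlates with prevalence. It is, however, already planned for every cluster, whereas pre-intervention survey prevalence is not: Protocol 7.4.6 funds post-distribution surveys in 12 areas only.

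**Conclusion.** The concern holds. The survey models omit the randomisation block and the baseline term that the primary model includes, without a stated reason. The consequence is lost precision rather than bias or a broken power claim.

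For an assumed district share of 0.2 to 0.6, the standard error is about 8% to 33% too large and type I error falls to between about 4% and 1%. The cluster-level power forgone at PR 0.72 is about 3 to 10 points. These figures assume 20% control prevalence, 90 children per cluster and CV 0.4. If district explains nothing, adding it costs about one point. The change should be made, but the secondary analyses are not invalid without it.

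**What to change.** In SAP 8.2.1 and Protocol 13.5:

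1. Add a random effect for district to every survey model, with cluster nested in district, and household nested in cluster where it is already specified.
2. Test the arm effect against t with 31 df (30 with a baseline covariate). Alternatively, name a paired cluster-level analysis of the 32 within-district differences. That is also a fallback if the three-level model does not converge, which has not been tested.
3. Do not use 32 fixed district intercepts with a cluster random effect and an uncorrected maximum-likelihood Wald test. The variance is then divided by 64 instead of 31, and the error rate is P(|t31| > 1.96 × √(31/64)) = P(|t31| > 1.36) = 18%.
4. For parasitaemia and anaemia, adjust for log baseline MRC incidence as in the primary model, and add this to SAP 9.2.
5. State what is used where three baseline months are not available. Both Moyo MRCs started in September 2020 (Protocol Table 2). Protocol 5.1 has the study districts "scheduled to receive nets from October 2020 to February 2021", while Protocol 4.1 and SAP 3.1 give November 2020 to March 2021. Moyo's own date is not given, so a shortfall is possible but not established. The two schedules should be reconciled.

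The cost is wording and one or two model terms, with no new data. The downside is one more variance component, about one point of power if district explains nothing, and one to two points if baseline incidence is unrelated to prevalence.

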## 8.3 Secondary outcomes from economic evaluation

The measure of effectiveness will be number of malaria case averted will be derived from incidence data, which will be calculated by dividing the number of laboratory-confirmed malaria cases diagnosed at each MRC (among patients residing in the target area per unit time) by the total population of the MRC target area [31-33]. All data analyses are addressed in the Health Economics Analysis Plan (HEAP).

## 9 General Considerations

---

All data will be analysed using STATA version 14.0 (Stata corporation, College Station, Texas).

### 9.1 Analysis Populations

All analyses will use an intention-to-treat approach where clusters will be analyzed according to the randomization scheme (as per Appendix A).

### 9.2 Covariates

In the primary analysis of the primary outcome (malaria incidence) we will adjust for cluster level baseline estimates of malaria incidence (3 months prior to the intervention). In secondary analyses of the primary outcome we will adjust for additional cluster-level covariates from the cross-sectional surveys including treatment seeking behaviour (to account for cases of malaria not captured at the MRCs) and the diagnostic accuracy of RDTs vs microscopy (to account for differences in the use of these diagnostic tests between clusters).

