A detailed description of the informed consent procedures is provided in section 14.2. Briefly, study personnel will carry out the informed consent discussion with the adult or parent(s) or guardian(s) of children. Informed consent will be conducted in the appropriate language and a translator will be used if necessary. Consent forms will be available in English and the local languages. Following the informed consent discussion, adults or parents/guardians will be asked by the study personnel to sign a written consent form to participate, or for their child(ren) to participate, in a research study (consent forms #2 & #6) and a second approved consent form for the future use of biological specimens obtained during the study (consent forms #3 & #7). Written assent to participate in the study will also be obtained from children aged 8 years and older at the time of screening (consent form #4). If an adult respondent or parent/guardian is unable to read or write, their fingerprint will substitute for a signature, and a signature from a witness to the informed consent procedures will be obtained.

7.4.4 *Clinical survey procedures*

The clinical surveys will be carried out by study personnel, including teams consisting of one clinician plus one research assistant. The surveys include measurement of temperature, subjective fever and a finger-prick blood sample for measurement of thick blood smear and haemoglobin (in children < 5 years), and storage of blood on solid phase media such as filter paper (Appendix H).

7.4.5 *Management of ill participants*

Participants who have a temperature of $\geq 38.0^{\circ}\text{C}$, or who report fever in the past 48 hours, will have an RDT performed by study personnel. Febrile participants will be treated with paracetamol as appropriate. Participants with a positive RDT and no evidence of severe malaria will be treated with artemether-lumefantrine (AL), which is the first-line recommended treatment for uncomplicated malaria in Uganda. Participants with a positive RDT and evidence of danger signs of severe disease will be referred for further evaluation and treatment. Any participant with other concerning clinical symptoms will also be referred to an appropriate health care facility at the discretion of the study personnel.

7.4.6 *Number and timing of surveys*

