11.4 Rapid diagnostic tests

Rapid diagnostic tests for malaria (RDTs) will be performed in the field on cross-sectional survey participants who are found to have a temperature of $\geq 38.0^{\circ}\text{C}$, or who report fever in the past 48 hours. RDTs will be performed according to the directions provided for the specific tests, using the blood transfer device and reagent provided by the manufacturer. Tests will be performed by study personnel, and results will be available within 15 minutes. The results of the RDT will be provided to the participant's caregiver verbally, and will be recorded on the appropriate case record form. Participants who test positive for malaria, and who are deemed to have uncomplicated disease, will be provided a full course of antimalarial treatment, and will also be counselled to go to the nearest health facility immediately if their condition worsens. Any participant with evidence of danger signs of severe malaria, or other concerning clinical symptoms, will also be referred to an appropriate health care facility at the discretion of the study personnel.

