### 5.2 Health facility-based surveillance

At each MRC (Appendix A), individual-level data from standardised registers for all patients presenting to the outpatient departments are entered into an Access database by on-site data entry officers. Primary data captured comes from the HMIS 002 standardised form (Appendix C) and includes location of residence (parish and village), age, gender, body temperature, history of subjective fever, type of malaria test done (rapid diagnostic test or microscopy), malaria diagnostic test results, any diagnoses given, and any treatments prescribed. Data from each MRC will be submitted to the team in Kampala on a monthly basis using a secure on-line system. Standardised data checks will be applied to assess for missing data and data errors. Data queries will be submitted back to the sites and corrected whenever possible. Interval data submitted from the MRCs will be merged into an existing master database. Each time the master database is updated, existing programmes will be run to perform variable transformations and generate standardised indicator variables.

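### The covariate meant to adjust for which malaria test each MRC uses measures RDT accuracy in the surveys, which is a different and imprecisely estimated quantity; the register's test-type field fits the purpose

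*SAP*

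**What the plan says.** SAP 9.2 states that in secondary analyses of the primary outcome "we will adjust for additional cluster-level covariates from the cross-sectional surveys including treatment seeking behaviour" and "the diagnostic accuracy of RDTs vs microscopy (to account for differences in the use of these diagnostic tests between clusters"). SAP 8.1.1 says the same and keeps the primary model to baseline incidence alone. Protocol 13.5 has no such division. Of the primary-outcome model it says "We will also adjust our model for baseline estimates of malaria incidence (3 months prior to the intervention) and additional cluster-level covariates", and it then lists the same two survey covariates.

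Every clinical-survey participant has a thick smear, but not every participant has an RDT. Protocol 11.4: "Rapid diagnostic tests for malaria (RDTs) will be performed in the field on cross-sectional survey participants who are found to have a temperature of" 38.0°C or more, or who report recent fever. Protocol 7.4.5 gives the same rule: those with that temperature, "or who report fever in the past 48 hours, will have an RDT performed by study personnel". Of the survey RDTs, Protocol 11.4 says: "Tests will be performed by study personnel, and results will be available within 15 minutes". Under Protocol 11.1 survey smears go to the central laboratory in Kampala, where each has a second reading and a third reader settles disagreements. The survey procedures in SAP 5.3.7 list no RDT.

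For the MRCs, the outpatient data described in Protocol 6.1 and SAP 5.2 include "type of malaria test done (rapid diagnostic test or microscopy") together with the result.

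Neither document says which accuracy measure is meant, which survey round supplies it, or what is done for a cluster with few or no paired results.

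**The concern.** The stated purpose is to deal with clusters that use the two tests in different proportions. If RDTs and microscopy classify patients differently, the test mix at an MRC shifts its confirmed case count, and an imbalance between arms would shift the incidence rate ratio. An adjustment for this has to contain the mix. Survey RDT accuracy does not, and it comes from other operators, other readers and a different group of people from those tested at the MRCs.

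A second difficulty is sparse data. Only febrile participants contribute a pair of results, so each cluster's accuracy figure may rest on very few people. What is at stake is the reading of the adjusted analysis: it would be reported as having accounted for diagnostic differences when the covariate carries no direct information on test use.

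**Working it through.** **1. Purpose against covariate.** This step needs no assumed figure.

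| | Needed for the stated purpose | Planned covariate |
|---|---|---|
| Quantity | share of tests done by RDT | agreement of RDT with microscopy |
| Who is tested | MRC outpatients | febrile survey participants |
| RDT done by | the MRC | study personnel |
| Microscopy | the MRC's own | central, double-read |
| Source | outpatient register | community surveys |

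**2. Children per cluster.** SAP 6.2: "Assuming an average of 1.8 children aged 2-10 years per household, we estimate that we will survey 5,760 children from 3,200 households". Check: 64 × 50 = 3,200 households and 3,200 × 1.8 = 5,760 children, as stated. Per cluster, 5,760 / 64 = 90.

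**3. Paired results per cluster, one survey.** The febrile share f is not in the documents; I assume 5-30%. For smear positivity p, I apply figures from the protocol to febrile children, as an assumption. These are about 10% (10.6% in the PBO arm of the first LLINEUP trial at 12 months), 26% (2017 survey overall) and 53% (2017 survey, highest region).

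- Paired tests = 90f; smear-positives = 90fp.
- 95% half-width for an assumed sensitivity of 90% = 1.96 × √(0.9 × 0.1 / 90fp). At these counts it only indicates scale.
- Expected clusters with no smear-positive = 64 × (1 − fp)^90.

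| f | p | Paired tests | Smear-positives | Half-width (points) | Clusters of 64 with none |
|---|---|---|---|---|---|
| 5% | 10% | 4.5 | 0.45 | not meaningful | 41 |
| 10% | 10% | 9 | 0.9 | 62 | 26 |
| 10% | 26% | 9 | 2.3 | 38 | 6 |
| 30% | 26% | 27 | 7.0 | 22 | 0 |
| 30% | 53% | 27 | 14.3 | 16 | 0 |

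A half-width of 10 points needs 0.09 × (1.96 / 0.10)² = 34.6, so about 35 smear-positives per cluster.

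**4. With more data**, over the same ranges of f and p:

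- Both rounds, 180 children: 0.9 to 28.6 positives; best case ±11 points.
- All-ages clusters at 12 months, 50 × 5 = 250 people (5 per household is assumed): 1.25 to 39.8; best case ±9 points.
- All-ages clusters with the 24-month children added, 340 people: 1.7 to 54; best case ±8 points.

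The 32 children-only clusters stay below 35 even at the top of both ranges.

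**5. If accuracy means specificity.** With specificity assumed at 80%, the half-width is 1.96 × √(0.8 × 0.2 / 90f(1 − p)). This gives ±30 points at f = 10%, p = 26% (6.7 smear-negatives) and ±16 points at f = 30%, p = 10% (24.3).

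**6. How much test mix could matter.** Protocol 1.3 reports 30% positive by RDT and 19% by microscopy in one national survey, a ratio R = 30/19 = 1.58. That was a community survey of children aged 0-59 months, so it is only indicative for clinic patients. With RDT shares s1 and s0 in two groups, the spurious incidence ratio is [1 + s1(R − 1)] / [1 + s0(R − 1)]:

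- 90% against 80%: 1.521 / 1.463 = 1.04.
- 80% against 60%: 1.463 / 1.347 = 1.09.

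The design IRR is 0.74. With the larger RDT share in the PPF arm, a ratio of 1.09 would make it appear as 0.74 × 1.09 = 0.81. The documents report no such imbalance; these figures are an illustration of scale.

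**7. Accuracy pooled over clusters.** At f = 10%, p = 26%, one survey gives 64 × 9 = 576 pairs and about 150 smear-positives. Sensitivity is then known to about 1.96 × √(0.09 / 150) = ±5 points, ignoring clustering.

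**The case against.** There are several fair points in the plan's favour.

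- **Sparse data.** A reader might infer that accuracy cannot be estimated per cluster at all. The documents do not support that. They give no febrile share, smear positivity among febrile children may exceed the survey average, there are two rounds, 32 clusters enrol all ages at 12 months, and accuracy need not mean sensitivity. What stands is imprecision in most clusters, and sensitivity possibly undefined in some.
- **Accuracy as a conversion factor.** Test use is known from the register, so accuracy might be meant as a factor applied to it. That would be sensible, but SAP 8.1.1 and 9.2 describe a cluster-level covariate in a regression and do not mention the register test mix there.
- **Protection already in place.** Randomisation was within district, the sponsor aimed for comparable level of care within district, and baseline incidence comes from the same MRC testing, so it absorbs part of any stable difference in test mix. This limits the likely bias. It does not make the covariate suit its purpose, and it does not cover a mix that changes after distribution.
- **The replacement.** RDT share over follow-up is measured after randomisation and could respond to caseload or supplies. The planned covariate is post-randomisation too, but the point stands and shapes the fix.
- **Completeness.** The register has a test-type field, but the documents do not say how complete it is.

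**Conclusion.** The point holds, with limited reach. As written, the adjustment cannot do its stated job, because survey RDT accuracy contains no information on the mix of tests behind the MRC case counts. That conclusion follows from the text and rests on no assumed figure.

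The precision argument is secondary and rests on an assumed febrile share of 5-30% and borrowed smear positivity of 10-53%. One survey then gives 4.5-27 paired results and 0.5-14 smear-positives per cluster, against about 35 needed for ±10 points on sensitivity.

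Two stronger inferences are not supported. One is that the primary result is compromised: under the SAP the primary model adjusts only for baseline incidence, so this touches a secondary analysis. The difference from Protocol 13.5 still has to be reconciled. The other is that the adjusted analysis would look reassuring whether or not test mix matters: nothing in the documents shows this, and no imbalance in test mix is reported.

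**What to change.** In SAP 8.1.1 and 9.2 and Protocol 13.5:

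1. Replace the covariate with the proportion of malaria tests done by RDT among tested target-area residents at each MRC, from the register test-type field.
2. Use the pre-distribution share. The three-month window already set for baseline incidence would serve. Report the follow-up share as a sensitivity analysis, with the caveat that it is measured after randomisation.
3. If accuracy is wanted, name the measure and the survey round, estimate it once over all clusters, and combine it with the register test mix as a fixed correction. State the assumption that survey accuracy carries over to the MRCs.
4. Make the two documents agree that this adjustment is secondary, or say otherwise.
5. Report the completeness of the test-type field by arm.

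The cost is wording and minor analysis work. Sample size and data collection do not change. The downside is reliance on a field whose completeness the documents do not state.
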